5.3.1 Important Protocol Deviations Leading to Exclusion from the PP Population Analysis

Only those important protocol deviations considered to have a major effect on efficacy will lead to complete exclusion of the patient from the PP population. For the purposes of this study, the following criteria have been identified as important protocol deviations leading to exclusion from the PP population as it is considered that the occurrences of any of these criteria might have an important influence on the primary efficacy endpoint.

Statistical Analysis Plan Final v3.0

Type	Important Protocol Deviation Leading to Exclusion from the PP population	Method of Identification
Prohibited Medication	Patients who take medications that are not permitted during the double-blind Treatment Period	Non-programmable review of blinded prior and concomitant medications listings Labcorp will provide the Medical Monitor with the lists of prior and concomitant medications taken by patients. The Medical Monitor will review this list and note any prohibited medications or therapies within 1 month prior to the Screening Visit. Patients will be excluded if they had prohibited medications or therapies within 1 month prior to the Screening Visit.
Entry Criteria Violations	Patients did not meet Inclusion Criterion 9 which is thought to impact efficacy	Programmatic check based on eligibility data
Noncompliance During 6-week Double-blind Treatment Period	Patients who had low study drug compliance rate (<80%)	Programmatic check based on exposure and drug accountability data
Minimum Treatment Duration	Patients did not receive at least 5 weeks of double-blind treatment	Programmatic check based on the exposure data
Week 6 ADPS Missing	Patients did not have at least 4 ADPS scores within Week 6 in order to calculate weekly ADPS	Programmatic check of ADPS data
Errors in Treatment Allocation	Patients who received a wrong treatment at 1 or more study visits due to packaging or dispensing errors during the double-blind Treatment Period	Programmatic check based on unblinded IRT database after the study is unblinded. The check will be done by comparing the kit number that IRT had assigned to the patient/visit against the kit number actually used.

CONFIDENTIAL

Statistical Analysis Plan Final v3.0

Lexicon Pharmaceuticals, Inc.
Protocol ID: LX9211.1.201-DPN

Labcorp Study ID: 000000198624

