Incorrect Stratum used in Randomization	Patients were randomized using an incorrect stratum	Programmatic check of IRT database compared to ADPS from Run-in
Clinical Trial Management System	Labcorp Clinical will provide the list of protocol deviations based on the clinical monitoring.	Non-programmable: The list will be reviewed prior to database lock and unblinding, and the important protocol deviations leading to exclusion from the PP population will be identified.

As defined in the table, a set of the important protocol deviations leading to exclusion from the PP population will be determined programmatically from the data. Those criteria which require clinical or medical monitoring interpretation will be reviewed prior to database lock.

All important protocol deviations occurring during the study will be reviewed and approved by Lexicon Pharmaceuticals, prior to database lock unblinding. Should additional important protocol deviations leading to exclusion from the PP population, not anticipated at the time of preparing this SAP, be identified during the study (and prior to unblinding), they will be provided in a separate document and included in all relevant protocol deviation reviews and approvals.

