7.3 Protocol Deviations

All-important protocol deviations leading to exclusion from the PP population (see [Section 5.3.1](#)) will be listed and summarized by study drug group for the mITT population.

The deviations will be identified before data are unblinded.

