7.8 Interim Analysis

Enrollment will not be temporarily halted while data for the interim analysis is being reviewed.

An interim analysis of the primary endpoint will be performed to test for futility when approximately 50% of the planned information has been achieved. This will occur when the first 141 patients have been accrued and followed to endpoint at Week 6 or dropped out from the trial earlier, whichever event occurs first. Should a patient drop out early in the study, but return for the Week 6 visit, the Week 6 data will be used in the analysis.

To maintain continuous blinding and study integrity, analysis will be conducted by a separate unblinded team. Details of the unblinding process for the interim analysis and the resulting controlled dissemination of interim analysis data will be detailed in the Data Monitoring Committee (DMC) Charter document.

A non-binding futility boundary will be used to test treatment group differences in the primary endpoint at 50% of the original planned information. The set of boundary values will be derived by using a beta spending function and specification of a power family with value = 3.672. The monitoring boundary is constructed by assuming a 1-sided test with a per comparison Type I error rate = 0.0141, assuring an overall $\alpha = 0.025$ (or a two-sided $\alpha = 0.05$) for the two LX9211 versus placebo comparisons. Use of this beta spending function for futility testing is conservative and results in cumulative beta error rates of 0.015 and 0.197 at the interim and final analyses, respectively. Application of the futility analysis is to serve as a guideline and is not the only source of information used to evaluate the trial for a negative finding. Assessment of other data available at the interim analysis will be used to qualify the trial for a recommendation of futility (eg, secondary and other efficacy variables, safety data).

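### The per-protocol exclusion for treatment-allocation errors is identified after unblinding, against SAP 7.3, by a kit-number test that does not match its own criterion of wrong treatment

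*SAP*

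**What the plan says.** SAP 5.3.1 lists the deviations that remove a patient completely from the PP population. The row on errors in treatment allocation has two parts.

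- **Criterion:** "Patients who received a wrong treatment at 1 or more study visits due to packaging or dispensing errors during the double-blind Treatment Period".
- **Method of identification:** "Programmatic check based on unblinded IRT database after the study is unblinded. The check will be done by comparing the kit number"; in full, the comparison is described as "comparing the kit number that IRT had assigned to the patient/visit against the kit number actually used".

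Two other statements set the timing for PP exclusions.

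- After the table, SAP 5.3.1 states: "All important protocol deviations occurring during the study will be reviewed and approved by Lexicon Pharmaceuticals, prior to database lock unblinding".
- SAP 7.3 refers to the deviations leading to PP exclusion, points back to 5.3.1, and states: "The deviations will be identified before data are unblinded".

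Neither statement exempts the allocation row. On the use of the PP set, SAP 7.6 says in general terms that supportive analyses will be done on it, and SAP 7.6.1 specifies a repeat of the primary MMRM. The primary analysis itself uses mITT, with patients analysed as randomized (SAP 5.2 and 7.6).

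**The concern.** There are two separate problems in one table row.

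The first is timing. If this exclusion is identified only after unblinding, the PP set is incomplete at the moment the arms become known. A supportive analysis is most useful when its population was closed blind, and SAP 7.3 promises exactly that. A programmer who follows the row breaches 7.3, and one who follows 7.3 cannot carry out the row.

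The second is measurement. The criterion concerns which treatment the patient received, while the test concerns which number was on the kit. The two can disagree in either direction, so the set of patients flagged need not be the set that the criterion describes. One mismatch at a single visit is enough for complete exclusion.

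**Working it through.** No figure in the plan is at issue, so the check is mainly a comparison of texts.

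**Timing**

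| Place | When PP exclusions are settled |
|---|---|
| SAP 5.3.1, allocation row | After unblinding, from unblinded IRT data |
| SAP 5.3.1, clinical trial management row | Before database lock and unblinding |
| SAP 5.3.1, text after the table | Sponsor review and approval of all important deviations before unblinding |
| SAP 7.3 | Before unblinding, for all the 5.3.1 exclusions |

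A deviation first found after unblinding can satisfy neither of the last two rows. The text after the table does separate criteria determined programmatically from those needing clinical interpretation, and says the latter are reviewed before lock. That is not an exemption for programmatic criteria: the approval sentence covers all important deviations, and 7.3 makes no distinction.

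**Test against criterion**

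| Event | Right treatment received? | Result of kit-number test | Result the criterion calls for |
|---|---|---|---|
| Assigned kit used, contents correct | Yes | Pass | Keep |
| Different kit, same content | Yes | Flag | Keep |
| Different kit, different content | No | Flag | Exclude |
| Assigned kit used, contents wrong (packaging error) | No | Pass | Exclude |

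The second and fourth events are misclassified. The fourth matters because the criterion names packaging errors.

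**Does the test need unblinded data?** Comparing one kit number with another does not need the arm. Only looking up the content of a mismatched kit does, and the row does not write that step. As written, the row therefore gives no reason to wait for unblinding.

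**Can the number of misclassified patients be estimated?** Not from the documents. As an illustration, let e be the kit-mismatch rate per dispensing visit, and s the share of mismatched kits that hold the assigned content. Double-blind drug is dispensed at three visits (Day 1, Week 2 and Week 4 in the schedule of events). Out of the planned 282 patients:

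- flagged = 282 × [1 − (1 − e)³]
- truly given wrong content at least once = 282 × [1 − (1 − e(1 − s))³]
- correctly treated but flagged = the difference between these two

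| e (assumed) | Flagged | Correctly treated but flagged, s = 1/3 | Correctly treated but flagged, s = 2/3 |
|---|---|---|---|
| 0.1% | 0.85 | 0.28 | 0.56 |
| 0.5% | 4.21 | 1.40 | 2.80 |
| 1% | 8.38 | 2.77 | 5.57 |
| 2% | 16.58 | 5.45 | 10.98 |

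Both e and s are assumptions, and the answer runs from well under one patient to about 11. The supply design does not fix s either. Maintenance tablets differ in all three arms, so a random draw from equal stock would give s = 1/3. Loading tablets are only 50 mg or placebo and come in bottles of two (Protocol 7.1.2 and Table 7.4-1). If each loading dose is two bottles, the three arms together use 1 + 2 + 0 = 3 active and 1 + 0 + 2 = 3 placebo bottles, so the same draw would give s = 3/6 = 1/2.

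**The case against.** The strongest reply is that the row is loosely worded but harmless. It has three parts.

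- **The check is pre-specified and programmatic.** No judgement is written into it, and the discretionary routes close earlier: criteria needing clinical interpretation are reviewed before lock, and any further exclusion criteria must be identified before unblinding. This stands. A reader might infer that PP membership could be steered by the results, but the documents do not support that. The row places the check after unblinding, not after results are available, and it applies a fixed rule to dispensing records. What remains is that the SAP breaks its own timing rule.

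- **A content lookup may have been intended.** The criterion column says wrong treatment, and an unblinded database would be needed only to look up contents. SAP 5.3.1 also reserves exclusion for deviations with a major effect on efficacy, which a same-content swap would not have. This stands in part. A reader might infer that correctly treated patients will be dropped; the documents show only that the literal method could do so. The lookup is still not written, and it would not catch a correctly numbered kit with wrong contents.

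- **A pre-lock check is not free.** The separate unblinded team in SAP 7.8 is described for the interim analysis, and Protocol 6.7 restricts release of the randomization schedule until study end. This stands as a cost. It is not a bar, because a yes/no flag from a party that is already unblinded does not release the schedule.

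**Conclusion.** The timing contradiction is certain on the text: SAP 5.3.1 (allocation row) cannot be followed together with SAP 7.3 and the approval rule in 5.3.1, so PP membership is not final when the arms become known. The mismatch between test and criterion is also real, but its effect is a possibility that depends on applying the method literally.

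The reach is small. Only the supportive PP analysis is affected, chiefly the PP repeat of the primary MMRM. SAP 7.6.2, 7.6.3 and 7.6.4 name mITT for the secondary, sensitivity and subgroup analyses, and the mITT primary result does not change.

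No number of affected patients can be given, since the documents report no error rate. A reader might infer that one third of flagged patients would be excluded wrongly, from the 1:1:1 allocation. That rests on random picking from equal stock, which the documents do not state, and the loading-dose supply alone would give a different share under the same assumption.

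**What to change.** Rewrite the method cell of the allocation row in SAP 5.3.1 so that it agrees with 7.3:

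1. Before database lock, compare assigned and used kit numbers on blinded data.
2. For each mismatch, and for each reported packaging error, an independent unblinded party confirms whether the content differed from the assigned treatment. It returns only a yes/no exclusion flag, which does not disclose the arm. The SAP should name and authorise this party, for example the existing unblinded team.
3. A mismatch with the same content does not lead to exclusion.
4. PP membership is frozen before unblinding.

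The cost is one small pre-lock task and the authorisation for the unblinded party. No patients and no new data collection are needed.

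A lesser alternative is to write an explicit exception for this row into SAP 5.3.1 and 7.3. That would remove the contradiction, but PP membership would still be open at unblinding and the kit-number test would still not match its criterion.

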5.4 PK Populations

There are 2 PK populations as defined below.

5.4.1 PK Population - C_{trough}

The PK population for evaluation of C_{trough} will include all patients who receive at least 1 dose of study drug and have at least 1 C_{trough} sample collected.

5.4.2 PK Population - Substudy

The PK population for the PK Substudy will include patients who receive at least 1 dose of study drug and who have a predose sample and have at least the minimum of samples required to estimate the PK parameters.

5.5 Safety Population

The Safety population is defined as those randomized patients who take at least 1 dose of study drug during the double-blind Treatment Period. Safety patients are analyzed according to their actual treatment received on Study Day 1.

CONFIDENTIAL

Document Date: 07JUN2022

Page 17 of 55
ST-AD-008 version 05

6. Data Handling

6.1 Time Points and Visit Windows

Day 1 is defined as Baseline/Randomization visit, is also the first day that study treatment during the double-blind Treatment Period is planned to be started. Should study treatment start at a later date, Day 1 will be defined as the date that study treatment during the double-blind Treatment Period is initiated. Relative days after Day 1 are calculated as (assessment date – Day 1 date) + 1. Relative days prior to Day 1 are calculated as (assessment date – Day 1 date). The day prior to Day 1 is Day -1; there is no Day 0.

6.1.1 Primary efficacy, secondary efficacy, and other efficacy endpoints based on daily pain diary data

The following visit windows defined in [Table 1.1](#) will be used for the analyses of the primary efficacy endpoint, the secondary efficacy and other efficacy endpoints based on the ADPS as well as for the secondary endpoint on pain interfering with sleep.

Table 1.1 Definition of time point windows for analyses based on ADPS and sleep interference rated each evening

Time point	Time point window ^a
Baseline	Day -7 to Day -1
Week 1	Days 1 to 7
Week 2	Days 8 to 14
Week 3	Days 15 to 21
Week 4	Days 22 to 28
Week 5	Days 29 to 35
Week 6	Days 36 to 42
Week 7	Days 43 to 49
Week 8	Days 50 to 56
Week 9	Days 57 to 63
Week 10	Days 64 to 70
Week 11	Days 71 to 77

^a relative to the date of first dose of study drug during the double-blind Treatment Period/date of Randomization/date of Baseline Visit (Day 1)

The Baseline value for ADPS based on Question 5 of the BPI-DPN will be calculated as the mean value of the corresponding question over Week 2 of the single-blind Run-in Period, provided that ≥ 5 days with non-missing data from that period are available for analysis. The Baseline value for the interference with sleep using Question 9F of the BPI-DPN will be calculated as the mean value of the

corresponding question over Week 2 of the single-blind Run-in Period, provided that ≥ 5 days with non-missing data from that period are available for analysis.

The post-Baseline values will be calculated as the mean value of the corresponding question, ie, Question 5 for ADPS and Question 9F for interference with sleep of the BPI-DPN, rated by patients each evening in the daily pain diary and collected during the target week period. A minimum of 4 non-missing data points within the target week period is required for the calculation of the mean value for that particular week.

6.1.2 Secondary efficacy and other efficacy endpoints based on data collected at clinic visits

The rest of the efficacy endpoints based on data collected at clinic visits will follow the visit windows defined in [Table 1.2](#).

Table 1.2 Definition of visit windows for efficacy data collected at each visit

Visit	Target Day of Visit ^a	Acceptable visit window
Screening	Day -28	NA
Run-in ^b	Day -14	NA
Baseline	Day 1	Day 1 to Day 4
Week 2	Day 15	Day 5 to Day 22
Week 4	Day 29	Day 23 to Day 36
Week 6	Day 43	Day 37 to Day 60
Week 11	Day 78	Day 61 to 35 days after the last treatment dose during the double-blind Treatment Period

^a relative to the date of first dose of study drug during the double-blind Treatment Period/date of Randomization/date of Baseline Visit (Day 1)

^b weight is collected

In general, the Baseline value for a variable is defined the last value collected or taken on or before Day 1 and prior to the first dose of double-blind study drug. In cases where there are multiple such values, the non-missing value closest to the start of study treatment is selected. If time is available for an assessment on Day 1, it will be compared with dosing time on Day 1 to define the Baseline value.

Multiple visits within the same window will be dealt with as follows:

- If both scheduled and unscheduled visits fall within the same visit window, the scheduled visit will be used for analysis.
- If multiple scheduled visits occur within a single visit window, then the visit closest to the target day of the visit window will be used in the analysis. If there is a tie, the later visit will be used in the analysis.

- If multiple unscheduled visits occur within a single visit window (with no scheduled visit within the window) then the unscheduled visit closest to the target day of the visit window will be used in the analysis. If there is a tie, the later unscheduled visit will be used in the analysis.

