Week/Visit Window (days)	Week -4	Week -2	Day 1 (Baseline) [a]	Week 2	Week 4	Week 6 Or EOT / EW	Week 11[b] Or 35 Days after EOT / EW
			+3	±3	±3	±3	+7
Record concomitant medications [f]	X	X	X	X	X	X	
Record SAEs [g]	X	X	X	X	X	X	X
Record AEs [h]			X	X	X	X	X
Dispense single-blind placebo		X				X	
Dispense double-blind study drug			X	X	X		
Patient Reported Outcome							
Dispense patient daily e-diary		X					
of BPI-DPN on e-diary each day and records rescue medication		•		Ongoing	0		
Review patient daily e-diary			X	X	X	X	X
Patient completes the full BPI-DPN			X	X	X	X	X
Patient completes PGIC						X	X
Patient completes NPSI			X			X	X
Laboratory Assessments							
A1C	X						
Serum chemistry	X		X	X	X	X	X
Hematology	X		X			X	
Urinalysis with microscopy	X		X	X	X	X	X
Pregnancy test (serum) [i]	X						
Pregnancy test (urine) [i]			X			X	
FSH (females only) [j]	X						
Urine drug test for drugs of abuse and cannabinoids	X		X				
and cannabinoids							

Exit Interview Substudy Assessments				
Exit interview [1]			X	

Abbreviations: A1C = hemoglobin A1C; AE = adverse event; BMI = body mass index; ECG = electrocardiogram; EOT = end of treatment; EW = early withdrawal; FSH = follicle-stimulating hormone; GFR = glomerular filtration rate; PK = pharmacokinetics; SAE = serious adverse event; IXRS = Interactive Voice/Web Response System; HADS = hospital anxiety and depression scale; BPI-DPN = brief pain inventory short form for diabetic peripheral neuropathy; PGIC = patient global impression of change

- a. Day 1 window is +3 days; All laboratory assessments occur prior to first dose of double-blind study drug.
- b. All patients will have a Safety Follow-up Visit 35 days/5 weeks after the last dose of study drug for collection of a plasma sample for LX9211 analysis, complete patient reported outcome assessments, and to record information on any serious adverse events (SAEs), any adverse event (AE) that was ongoing at the time of the Week 6 / EOT / EW visit, or any new events that have occurred.

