complete $\geq 70\%$ of the daily pain diary entries during the week prior to randomization, meet criteria for moderate to severe pain, and demonstrate $\geq 80\%$ compliance with taking the expected amount of placebo tablets during the Run-in Period. During the Run-in Period patients will not be allowed to use any rescue medication. On the morning of the Run-in Visit, patients may consume a light meal prior to the visit.

Note: Patients who fail Screening may be rescreened ONCE after discussion with the Medical Monitor.

Randomization/Double-blind Treatment Period: Patients who successfully complete the 2-week single-blind placebo Run-in Period and meet all other eligibility criteria will enter a 6-week double-blind Treatment Period.

Patients will be randomly assigned in a 1:1:1 ratio among the following 3 treatment groups:

- **Group 1:** LX9211 100 mg* / 10 mg**, once daily (qd)
- **Group 2:** LX9211 200 mg* / 20 mg**, qd
- **Group 3:** Placebo, qd

* Loading dose (Day 1)

** Maintenance dose (Day 2 – Week 6 Visit)

Implementation of the treatment randomization schedule will be centralized. A 1:1:1 ratio for assigning patients among the treatment groups will be accomplished by use of randomly permuted blocks of fixed size.

On Day 1, patients will receive 1 of 2 dose levels of LX9211 or placebo, based on their treatment assignment, to be given as a loading dose at the clinic. Patients will remain at the clinic for observation for 2 hours following dosing. At 2 hours ± 10 minutes, orthostatic vital signs will be obtained (heart rate and blood pressure) after which time patients may be released. The loading dose will be followed by a daily maintenance dose taken at home on Day 2 through the Week 6 Visit. **Note:** On days of the clinic visits, patients will refrain from taking their daily dose until after the visit.

Each evening during the double-blind Treatment Period, patients will be required to rate and record the severity of their DPNP over the previous 24 hours based on Question 5 of the BPI-DPN by answering the question "Please rate your pain due to your diabetes by indicating the one number that best describes your pain on the average." (0 [no pain] to 10 [pain as bad as you can imagine]), record the use of rescue medication (acetaminophen), and rate the interference of the patient's pain with sleep based on Question 9F of the BPI-DPN. The ADPS will be calculated using

CONFIDENTIAL

Document Date: 07JUN2022

Page 9 of 55

ST-AD-008 version 05

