all available data, however a minimum of 4 days (consecutive or non-consecutive) from the last week prior to each clinic visit is required for the calculation of weekly averages.

On the day of randomization, patients will also receive a bottle of acetaminophen. If a patient is unable to tolerate their DPNP, they are encouraged to discuss treatment options with the Investigator. At the Investigator's direction, the patient may be permitted to take acetaminophen (up to a maximum of 3 grams per day) as a rescue medication. If rescue medication does not provide adequate pain relief, the patient may discontinue from further participation in the study after consultation with the Investigator. Patients discontinuing the study prior to completion of the Week 6 Visit should also complete the Safety Follow-up Visit 5 weeks later.

Safety Follow-up Period: Following completion of the 6-week double-blind Treatment Period, all patients will enter the 5-week single-blind Safety Follow-up Period and take 1 tablet of single-blind study drug each morning during this period. During the 5-week single-blind Safety Follow-up Period, patients are allowed use of rescue medication (acetaminophen) if needed. Each evening patients will continue to rate and record the average severity of their DPNP over the previous 24 hours using Question 5 of the BPI-DPN and record the use of rescue medication (acetaminophen).

Blood samples for the determination of plasma LX9211 trough levels (C_{trough}) will be collected predose on Day 1, and at Weeks 2, 4, and 6 clinic visits, just prior to the dosing of study drug on the day of the visit. At the Week 11 EOT/EW Visit, a final sample will be collected.

Optional Substudies: During the Screening Visit, patients may choose to participate in 1 or both of 2 optional substudies.

The first substudy will include approximately 30 patients for intensive blood sampling for determination of LX9211 plasma concentrations to allow for PK parameter estimation, and additional samples for possible biomarker analyses. The PK intensive sampling will occur on Days 1 and 2 and at the Week 6 clinic visit. These patients will be confined to a clinical research unit (CRU) twice during the study for intensive PK evaluation and biomarker evaluation: prior to and following the first dose of study drug and prior to and following their final dose of study drug (planned for Week 6).

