Appendix 2: Schedule of Events

Week/Visit Window (days)	Screening Period (up to 2 Weeks)	Single-blind Placebo Run-in Period	Double-blind Treatment Period				Single-Blind Safety Follow- up
	Visit 1 Week -4	Visit 2 Week -2	Visit 3 Day 1 (Baseline) [a]	Visit 4 Week 2	Visit 5 Week 4	Visit 6	Visit 7 Week 11[b] Or 35 Days after EOT / EW
			+3	±3	±3	±3	+7
Initiation Activities							
Informed consent	X						
Confirmation of eligibility	X	X	X				
Medical history and demographics	X						
Register patient for Screening in IXRS	X						
Register patient for single-blind Run-in period in IXRS		X					
Register patient for Randomization in IXRS				X			
Procedures/Events							
Complete physical exam [c]	X						
Symptom-related brief physical examination [c]			X	X	X	X	X
Weight	X	X	X	X	X	X	X
Height	X						
BMI calculation	X						
Patient completes HADS	X						
MNSI (Part B)	X						
Seated vital signs	X		X	X	X	X	X
Orthostatic vitals [d]			X				
12-lead ECG [e]	X		X			X	X
Assess dose compliance			X	X	X	X	X

CONFIDENTIAL

Statistical Analysis Plan Final v3.0

Lexicon Pharmaceuticals, Inc.
Protocol ID: LX9211.1.201-DPN

Labcorp Study ID: 000000198624

Week/Visit Window (days)	Screening Period (up to 2 Weeks)	Single-blind Placebo Run-in Period	Double-blind Treatment Period				Single-Blind Safety Follow-up Period
	Visit 1	Visit 2	Visit 3	Visit 4	Visit 5	Visit 6	Visit 7
	Week -4	Week -2	Day 1 (Baseline) [a]	Week 2	Week 4	Week 6 Or EOT / EW	Week 11[b] Or 35 Days after EOT / EW
Record concomitant medications [f]	X	X	X	X	X	X	
Record SAEs [g]	X	X	X	X	X	X	X
Record AEs [h]			X	X	X	X	X
Dispense single-blind placebo		X				X	
Dispense double-blind study drug			X	X	X		
Patient Reported Outcome							
Dispense patient daily e-diary		X					
Patient completes Questions 5 and 9F of BPI-DPN on e-diary each day and records rescue medication			Ongoing				
Review patient daily e-diary			X	X	X	X	X
Patient completes the full BPI-DPN			X	X	X	X	X
Patient completes PGIC						X	X
Patient completes NPSI			X			X	X
Laboratory Assessments							
A1C	X						
Serum chemistry	X		X	X	X	X	X
Hematology	X		X			X	
Urinalysis with microscopy	X		X	X	X	X	X
Pregnancy test (serum) [i]	X						
Pregnancy test (urine) [i]			X			X	
FSH (females only) [i]	X						
Urine drug test for drugs of abuse and cannabinoids	X		X				
C _{total} blood samples [k]			X	X	X	X	X

CONFIDENTIAL

Document Date: 07JUN2022

Page 46 of 55
ST-AD-008 version 05

Statistical Analysis Plan Final v3.0

Lexicon Pharmaceuticals, Inc.

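### SAP Table 1.2 ends the Week 11 window on the first permitted day of Visit 7, omitting the schedule's +7 days, and leaves the window empty for last doses up to Day 25

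*SAP*

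**What the plan says.** The visit schedule (Protocol Appendix A, repeated in SAP Appendix 2) heads the Visit 7 column "Week 11[b] Or 35 Days after EOT / EW" and gives it a window of +7 days with nothing before. Footnote b ties the visit to dosing: "All patients will have a Safety Follow-up Visit 35 days/5 weeks after the last dose of study drug". Early stoppers are included: "Patients discontinuing the study prior to completion of the Week 6 Visit should also complete the Safety Follow-up Visit 5 weeks later" (SAP 2.2).

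SAP 6.1.2, Table 1.2, assigns clinic visits to time points by study day. Week 4 is Days 23 to 36. Week 6 is "Day 37 to Day 60", with target Day 43. Week 11 has target Day 78 and the window "Day 61 to 35 days after the last treatment dose during the double-blind Treatment Period". SAP 6.1.3 applies the same windows to laboratory, vital-sign, ECG and physical-examination data. If several scheduled visits share a window, "then the visit closest to the target day of the visit window will be used in the analysis". There is no rule for a scheduled visit that lies in no window.

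On dose timing, SAP 2.2 says "On days of the clinic visits, patients will refrain from taking their daily dose until after the visit", and also describes maintenance dosing as running to the Week 6 visit.

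**The concern.** The Week 11 row takes over the schedule's nominal 35 days but not its allowance. A patient seen 36 to 42 days after the last dose has complied with the protocol, yet the record belongs to no row of Table 1.2. Visit 7 is the only scheduled clinic visit after Week 6. It carries serum chemistry, urinalysis, vital signs, weight, ECG and the full BPI-DPN, and with a half-life of 6 to 8 days (Protocol 3.3) it is the off-drug read-out. Applied as written, the rule removes compliant records from the Week 11 tables, or else someone makes an undocumented programming decision to keep them.

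The same row fails differently for patients who stop early. Their follow-up visit can fall in the Week 6 row, so measurements taken about five weeks after the last dose would be tabulated with end-of-treatment safety data.

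**Working it through.** Inputs. L is the study day of the last double-blind dose. From Table 1.2: Week 4 is Days 23–36, Week 6 is Days 37–60, and Week 11 is Day 61 to Day L+35. From the schedule: Visit 7 may take place from 35 to 42 days after its anchor, which is 8 permitted days. I take footnote b's last dose to mean the last double-blind dose.

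The plan's own figure. The Week 11 target is 7×11+1 = Day 78, which also equals the Week 6 target plus 35 (43+35 = 78). It reproduces. With L = 42, however, the window closes on 42+35 = Day 77, one day before that target.

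The anchor can be read in three ways.

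- A, from last dose: permitted days are L+35 to L+42, and the window closes on L+35. For L of 26 or more, L+35 is at least 61, so 1 day is in Week 11 and 7 of 8 are in no window.
- B, from an EOT visit one day after the last dose: permitted days are L+36 to L+43, all after L+35. For L of 26 or more, 8 of 8 are in no window.
- C, fixed Days 78–85 with the last dose on the Visit 6 day (Day 43 ± 3, so L = 40–46): for L = 40, 41 and 42 the window closes on Days 75, 76 and 77, and 8 of 8 are outside. For L = 43, 44, 45 and 46 the counts outside are 7, 6, 5 and 4.

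Early stops. For L of 25 or less, L+35 is at most 60, so a window that opens on Day 61 is empty. Counting the 8 permitted days under A:

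| Last dose (L) | Permitted follow-up days | Week 4 | Week 6 | Week 11 | No window |
|---|---|---|---|---|---|
| Day 1 | 36–43 | 1 | 7 | 0 | 0 |
| Days 2–18 | L+35 to L+42, within 37–60 | 0 | 8 | 0 | 0 |
| Days 19 to 25 | L+35 to L+42 | 0 | 7 falling to 1 | 0 | 1 rising to 7 |
| Day 26 or later | L+35 to L+42 | 0 | 0 | 1 | 7 |

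Under B the pattern moves by one day: all 8 days fall in Week 6 for L = 1–17, 7 falling to 1 for L = 18–24, and none from L = 25.

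Competition with a true Week 6 visit. If an early stopper also attends on Days 40–46, that visit is at most 3 days from Day 43. Under A the earliest follow-up day for L = 12 is 47, which is 4 days away, so the follow-up cannot be chosen from L = 12 onward. It can be chosen only for L = 1–11.

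Checking the repair. With the upper limit at 42 days after the later of last dose and EOT visit, no permitted day lies outside every window under A or B for any L from 1 to 46. With the limit at L+42 alone, A is clean, but B loses Day L+43, which is 1 of 8, from L = 18 onward (18+43 = 61). Under C the new limit is Visit 6 day + 42. Visit 6 on Day 40, 41 or 42 gives Day 82, 83 or 84 and leaves 3, 2 or 1 days outside; Days 43–46 leave none.

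**The case against.** The best case against is that this matters little. The primary and diary endpoints use Table 1.1. Inferential secondary analyses stop at Week 6 (SAP 7.6.2). Safety has no formal tests (Protocol 10.4.5), adverse events are summarised by treatment period rather than by Table 1.2, and collected data are listed. A visit held exactly 35 days after the last dose loses nothing. All of this stands and limits the point to descriptive by-visit output.

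The 8-of-8 count also needs care. Dosing is described as running to the Week 6 visit, and the PK substudy samples before and after a final dose planned for Week 6. A last dose on the visit day is therefore at least as plausible as one the day before. The one-day lag is possible, because the dose is held until after a visit and Visit 6 dispenses single-blind placebo, but it is not established.

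Assignment by study day is a legitimate convention, and a nominal follow-up label pools a wide range of days. That is a real cost of the second change below.

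A reader might infer three stronger things that the documents do not support:

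- That early stoppers' follow-up visits in general land in Week 6. Counted from last dose, this is true of all permitted days only for last doses on Days 2–18 and of some for Day 1 and Days 19–25. It never happens from Day 26.
- That most Week 11 data will be lost. The 7 of 8 counts calendar days, not patients or records.
- That Week 6 clinic efficacy is corrupted. SAP 7.6.2 expressly admits observations after discontinuation of study drug, so those records are there by design.

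**Conclusion.** The conflict is clear on the face of the documents: the Week 11 upper limit omits the +7 days that the schedule allows. The result rests on reading Table 1.2 literally and, for the 7-of-8 figure, on counting Visit 7 from the last dose as footnote b does. Every reading of the anchor leaves at least 4 of 8 compliant days in no window for patients treated to Week 6.

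The outputs touched are the by-visit Week 11 summaries of laboratory data, vital signs, weight, ECG and clinic BPI-DPN, and the Week 6 safety rows (Week 4 for one day when the last dose is on Day 1) for patients who stopped by Day 25. The share of Week 11 records lost could be anything from 0%, if every visit is exactly 35 days after the last dose, to 100%. The documents give no visit timing, stop-day distribution or return rate, so the number of patients cannot be derived. Severity is minor to should-fix: small in consequence, but the stated rule is wrong and easily repaired.

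**What to change.** 1. In Table 1.2, set the Week 11 upper limit to 42 days after the later of the last double-blind dose and the Week 6/EOT/EW visit. Using the last dose alone is not enough if the EOT visit comes a day later.

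2. In SAP 6.1.3, state that by-visit safety summaries assign the scheduled Visit 7 by nominal visit to a time point labelled Week 11 / 35-day follow-up, and keep it out of the Week 4 and Week 6 safety rows. The first change does not correct the early stops; this one does, for safety only. The price is that the label would span study days from 1+35 = 36 to 46+42 = 88.

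3. If Week 11 is meant as fixed Days 78–85, the 1 to 3 days still outside the new limit stay uncovered for clinic BPI-DPN. To cover them, use nominal Visit 7 in the Week 11 BPI-DPN summary as well, for patients who reached Week 6.

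The cost is one table cell, one or two sentences and a small programming change. No new data are needed.
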